03/27/17

Spectrophon Dehydration Body Monitor Accuracy Study

NCT03229109

Authors:

**[name], [name],
[name], [name]**

1. *Kiryat Carmel Hospital, Israel*
2. *Ariel University, Israel*
3. *Spectrophon LTD, Rehovot, Israel*
4. *Maale HaCarmel Mental Health Center, Israel*

Protocol date: 03/27/2017, ver.: 3

-2017-

1. Study protocol

Healthy adults (n=200) in different age and gender groups were recruited for the study.

Samsung Gear S2 smartwatch with Spectrophon DBM attached to the bottom of the smartwatch were placed on the right wrist of each participant. At the same time, Samsung Gear Fit2 sport band with Spectrophon DBM attached to the bottom of the band was placed on the left wrist of the participant. Each participant was subjected to moderate physical activity. Data from Samsung Gear S2 and Samsung Gear Fit2 was obtained simultaneously. In parallel, subject weight was also monitored using commercially available digital balancers (Shekel B-200-P).

The evaluation of the measurement accuracy of the Spectrophon DBM was defined as the difference between subject weight change during the exertion (due to sweating and water consumption) and the volume of sweat detected by Spectrophon DBM.

All experiments were conducted indoors under ambient temperature (18°C) and humidity (40-60%) .

1.1. Experimental groups:

Number of subjects: 200 Age range: 18-50+

18-25 years: 50 participants 26-35 years: 50 participants 36-45 years: 50 participants 46-50 years: 50 participants

1.2. Inclusion criteria:

1. Age: older than 18, both gender.
2. Ability and willingness to sign an informed consent form for participation in the study.

Exclusion criteria:

1. Presence of cardiologic or vascular disease.
2. Evidence of any other serious medical disorder.
3. Pregnancy

2. Procedures:

Participants were weighed prior to the experiment (no clothing after maximal drying) and then subjected to physical activity (walking on the treadmill).

2.1. Activity protocol:

T0: Initiate exercise

T1: T0+15 min - Stop exercise, Rest T2: T0+25 min - Initiate exercise

T3: T0+40 min – Stop exercise, Rest T4: T0+50 min - Initiate exercise T5: T0+65 min – Stop exercise

T6: T0+75 min - Initiate exercise T7: T0+90 min – Stop exercise

Total duration of study: 90min.

2.2 Intensity of exercises:

Participants could choose high or low intensity of exertion: **a. High:** 0:00-0:01 – preparation; 0:01-0:05 – 5.5km/h;

0:05-0:10 – 6.0km/h;

0:10-0:15 – 6.5km/h;

b. Low: 0:00-0:01 – preparation; 0:01-0:05 – 5.0km/h;

0:05-0:10 – 5.5km/h;

0:10-0:15 – 6.0km/h;

2.3 Data recording:

After DBM application was activated, DBM started recording data (sweat rate and total salt in sweat) every 20 sec. and automatically saved results into archive on a mobile phone linked to Samsung Gear S2 or Samsung Gear Fit2 by Bluetooth. Manual recording of data was conducted during breaks (between phases T1-T2, T3-T4, T5-T6 and after T7).

Participants were also weighed during each break (no clothing after maximal drying).

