2.4. Drinking

During the procedure, subjects could drink up to 500 ml of water. The weight of the bottle was measured and recorded after drinking during breaks. The difference was subtracted to the weight loss calculation.

2.5 Restrictions:

In this experiment, we avoided:

1. Urination during test (empty before T0)
2. Weight loss should not exceed 2%

Participants could cancel the experiment at any point of the procedure if desired.

3. Statistical analysis

Data obtained from Spectrophone DBM will be compared to the subject's total weight loss for every participant. The measurement error distribution will be estimated.

Principal investigator

[name]

Signature

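### The spread of the reported DBM error includes an unquantified contribution from the weighing reference, because the plan assigns all disagreement to the device

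*Combined protocol and SAP*

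**What the plan says.** Section 1 gives the accuracy definition: "The evaluation of the measurement accuracy of the Spectrophon DBM was defined as the difference between subject weight change during the exertion", and the sweat volume from the DBM. The reference instrument is named in the same section: "subject weight was also monitored using commercially available digital balancers (Shekel B-200-P". No resolution, repeatability or calibration is given for it.

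On the weighings, Section 2 says "Participants were weighed prior to the experiment (no clothing after maximal drying") and Section 2.3 says "Participants were also weighed during each break (no clothing after maximal drying"). Neither says how many readings make up one weighing. Section 2.3 also places manual data recording at the three rests and after T7. Section 2.4 brings a second weighing into the reference through the drinking correction: "The weight of the bottle was measured and recorded after drinking during breaks". The balance used for the bottle and its precision are not stated.

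Section 3 is two sentences long. It compares DBM data with each participant's total weight loss and adds that "The measurement error distribution will be estimated". It has no term for reference error.

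**The concern.** The definition treats weight change as if it were known exactly. In fact it is a small difference between two large body weights, and it carries the random error of both weighings plus that of the bottle correction. All of this passes into what is reported as DBM measurement error.

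The error distribution is the only output that Section 3 names, so its spread is a main result of the study. If part of that spread belongs to the scale, the device looks less precise than it is. As written, the plan gives no means of saying how large that part is.

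**Working it through.** The plan states no SD, precision target, acceptance limit or power figure, so there is nothing of its own to reproduce. The check is error propagation.

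**Model.** Let D be the DBM volume minus the reference loss, where the reference is weight before, minus weight after, with the water correction. Let s be the SD of one body-weight reading. If the errors are independent,

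Var(D) = Var(device) + 2s² + Var(bottle).

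The observed spread therefore cannot be smaller than the device's own. The mean of D behaves differently: a constant scale offset cancels in before minus after, and zero-mean random error averages out. In a simulation with s = 20 g, a true device SD of 40 g and 200,000 draws, the mean difference was 0.15 g while the observed SD was 48.9 g. The formula gives √(40² + 2·20²) = √2400 = 49.0 g.

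**Inputs, all assumed.** Scale resolution d of 10, 20, 50 or 100 g; device SD of 20, 40 or 80 g; rounding as the only scale error; bottle error zero. For a given resolution and device SD, the last two make the result a lower bound.

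**Formulae.** The rounding SD of one reading is d/√12, so the SD of a difference is d/√6. Inflation of the SD is √(SD² + d²/6)/SD − 1. For example, with d = 100 g and device SD 40 g: √(1600 + 1667) = 57.2 g, and 57.2/40 − 1 = 42.9%.

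| Resolution | Reference SD (d/√6) | Device SD 20 g | Device SD 40 g | Device SD 80 g |
|---|---|---|---|---|
| 10 g | 4.1 g | +2.1% | +0.5% | +0.1% |
| 20 g | 8.2 g | +8.0% | +2.1% | +0.5% |
| 50 g | 20.4 g | +42.9% | +12.3% | +3.2% |
| 100 g | 40.8 g | +127% | +42.9% | +12.3% |

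**What duplicate readings buy.** With two independent readings averaged at each time, the reference variance is s²/2 + s²/2 = s² instead of 2s². At s = 28.9 g and device SD 40 g, the observed SD falls from 57.2 g to √(1600 + 833) = 49.3 g, and inflation falls from 42.9% to 23.3%.

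**How much to subtract.** The within-pair variance s² is computed from displayed readings, which are already rounded. When the duplicates vary, it therefore already contains the rounding error, and subtracting d²/6 as well counts rounding twice. In simulations with a true device SD of 45 g, losses of 300 to 600 g and reading noise of 20 to 50 g (all assumed), subtracting both terms gave about 40 g at 50 g resolution and about 19 to 24 g at 100 g resolution. Subtracting s² alone gave 45 to 47 g in the same settings. When duplicates are essentially identical, s² is near zero and misses rounding; d²/6 is then the appropriate allowance.

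**The case against.** The strongest objection is that the point may be empty in practice. The scale model is named, its specification is outside the documents, and if it is fine and repeatable the effect on the total is negligible. That stands, and it is why the size is given only as a range over assumptions. It does not remove the gap, because the plan gives the reader no way to tell.

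A second objection is that no decision turns on this. The plan has no acceptance limit or hypothesis, and the error works against the device, so the result is conservative. That also stands, and it keeps the priority low. Over-correction would be the worse fault, since it would favour the device.

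A reader might infer several stronger things that the documents do not support:

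- *That each weight was a single reading.* The plan is silent on the number of readings; it neither states nor excludes replicates.
- *That the device error as a whole is inflated.* Only the spread is. Random scale error and a constant offset leave the mean unaffected.
- *That per-break comparisons are badly distorted.* A change over one bout is also a difference of two weighings, on a smaller loss, so the relative effect would be larger. But Section 3 states only a comparison with total weight loss.
- *That a second reading removes all reference error.* Moisture left on the skin is the same when a person steps off and straight back on, so it does not enter the within-pair variance. Nor does bottle-weighing error.

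The two DBM units worn at once offer another route: the covariance of their differences estimates the reference variance. This holds only if the units' errors are independent; any error they share would be credited to the scale. Duplicate readings avoid that assumption.

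**Conclusion.** The concern holds in a limited form. The plan attributes all disagreement between DBM and weight change to the DBM, and describes no scale precision, replicate weighings or variance separation. The SD of the reported error, and any limits of agreement derived from it, therefore contain an unknown share of reference error; the mean error does not suffer from this.

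Under the rounding-only assumption the inflation runs from about 0.1% to about 127% across the ranges tried. It is about 2% or less when the resolution is 20 g or finer and the device SD is 40 g or more. The direction rests on scale error being independent of DBM error. The size rests wholly on assumed values for resolution and device SD. This is an inexpensive improvement, not a flaw that undermines the study.

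**What to change.** At least at the baseline and final weighings, which determine the total, read the scale twice, with the participant stepping off and on, and use the mean. Estimate s² from the displayed pairs as the sum of squared within-pair differences divided by twice the number of pairs.

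In Section 3, report the error SD raw and after subtracting s², which is the reference variance for a difference of two two-reading means. Do not also subtract resolution²/6 when the duplicates vary. Use resolution²/6 as the rounding allowance only when they are essentially identical. State the scale's resolution beside the result, and say that residual moisture and bottle-weighing error remain in the adjusted SD.

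The protocol describes recruitment and weighing in the past tense. If weighing is already complete, run a repeatability check on the same scale and report it beside the raw SD; where each recorded weight was one reading, the matching reference variance is 2s².

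The cost is one extra reading per weighing and one extra line of analysis. If duplicates are also taken during the 10-minute rests, those breaks become slightly longer.

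### The weight-loss reference counts respiratory water and net CO2/O2 mass as sweat, which overstates sweat in one direction by an amount the plan does not allow for

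*Combined protocol and SAP*

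**What the plan says.** Section 1 sets the accuracy measure as a difference between two quantities. The reference is "subject weight change during the exertion (due to sweating and water consumption"). The device side is "the volume of sweat detected by Spectrophon DBM". Section 2.3 describes the device output: "DBM started recording data (sweat rate and total salt in sweat) every 20 sec".

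Section 3 gives the analysis in two sentences: "Data obtained from Spectrophone DBM will be compared to the subject's total weight loss for every participant", and "The measurement error distribution will be estimated".

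The plan takes several steps to isolate sweat. Bottles are weighed to account for drinking (section 2.4), urination is avoided (section 2.5), and participants are weighed undressed and dried (sections 2 and 2.3). Respiratory water and gas-exchange mass are not mentioned, and no sensitivity analysis is named.

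**The concern.** One side of the comparison is whole-body mass and the other is sweat. The mass balance is

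sweat = weight loss + water drunk − respiratory water − net gas mass (CO2 out minus O2 in).

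The plan deals with the first two terms on the right and leaves out the last two. Their sum, L, stays in the reference and is read as sweat.

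The error distribution is the only planned output. With error taken as device minus reference, L moves the mean error by −L. A device that measured sweat exactly would look as if it under-read, and one that over-read by L would look unbiased. This is a systematic shift, so 200 participants estimate it more precisely but do not remove it. L also differs between people with body mass and chosen walking intensity, so it can add to the spread.

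**Working it through.** The plan has no figure on this point to reproduce. Only its schedule and room conditions can be used.

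**From the documents.** Section 2.1: walking 4 × 15 = 60 min and rest 3 × 10 = 30 min, together 90 min, as stated. Section 1: 18°C and 40-60% humidity.

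**Assumed (not in the documents).** Low / middle / high:
- ventilation walking 20 / 27.5 / 35 L/min, resting 8 / 10 / 12 L/min
- exhaled air saturated at 32 / 33.5 / 35°C, paired with room humidity of 60 / 50 / 40%
- O2 uptake walking 0.8 / 1.05 / 1.3 L/min, resting 0.25 / 0.30 / 0.35 L/min
- respiratory exchange ratio (RER) 0.80 / 0.875 / 0.95
- 1 ml of sweat weighs about 1 g

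**Step 1, respiratory water** = exhaled volume (m³) × (humidity of exhaled air − humidity of room air). By the Magnus formula, exhaled air holds 33.7 / 36.5 / 39.5 g/m³ and room air 9.2 / 7.7 / 6.1 g/m³.
- Low: (60×20 + 30×8)/1000 = 1.44 m³; × 24.5 = 35.3 g
- Middle: (60×27.5 + 30×10)/1000 = 1.95 m³; × 28.8 = 56.2 g
- High: (60×35 + 30×12)/1000 = 2.46 m³; × 33.3 = 82.0 g

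**Step 2, net gas mass** = litres of O2 × (1.977 × RER − 1.429).
- Low: (60×0.8 + 30×0.25) = 55.5 L; × 0.153 = 8.5 g
- Middle: (60×1.05 + 30×0.30) = 72.0 L; × 0.301 = 21.7 g
- High: (60×1.3 + 30×0.35) = 88.5 L; × 0.449 = 39.7 g

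**Step 3, total L over 90 min:** about 44 / 78 / 122 g.

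**Step 4, direction.** The gas term is positive when RER exceeds 32.00/44.01 = 0.727. At RER 0.70 it is −2.5 / −3.2 / −4.0 g, and the totals are still 33 / 53 / 78 g. The water term keeps L positive.

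**Step 5, body mass.** Let walking ventilation and O2 uptake scale with mass/70 kg (assumed). The middle value runs from 59 g at 50 kg to 106 g at 100 kg. The low case at 50 kg is 33 g and the high case at 100 kg is 167 g.

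**Step 6, a second set of assumptions.** Take O2 uptake walking 0.7 / 1.0 / 1.6 and resting 0.2 / 0.3 / 0.4 L/min, ventilation 22 / 25 / 28 L per L of O2, RER 0.80 / 0.87 / 0.95, exhaled air at 31 / 33 / 34°C and humidity 60 / 50 / 40%. The totals are 31 / 68 / 142 g.

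In round figures L is 30-170 g, with a middle near 80 g. This is not a bound: the low case at 50 kg with RER 0.70 gives 26.9 − 1.9 = 25 g.

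**Step 7, relative size.** The documents give no sweat volume, so the volumes below are also assumed.

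| True sweat | L = 30 g | L = 80 g | L = 170 g |
|---|---|---|---|
| 150 g | 20% | 53% | 113% |
| 300 g | 10% | 27% | 57% |
| 800 g | 4% | 10% | 21% |
| 1400 g | 2% | 6% | 12% |

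**The case against.** **The intended quantity may be mass loss.** The product is called a dehydration monitor, and section 3 openly names total weight loss as the comparator. If the device output was calibrated to whole-body weight loss, agreement with weight loss is the relevant result. This stands in part. Section 1 nevertheless states accuracy in terms of sweat volume, and the documents do not say how the device was calibrated. If it was calibrated to weight loss, the error describes agreement with weight loss and not accuracy for sweat.

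**Materiality is not shown.** This stands. Apart from the schedule and room conditions, every input is assumed. The plan gives no expected sweat volume, scale resolution or accuracy limit to compare with L. The relative error runs from 2% to over 100% in the table.

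**Subtracting a constant adds little.** This also stands in part. A constant slides the error distribution along its axis and leaves its spread unchanged, although the true term varies between people (59 to 106 g in the middle case from 50 to 100 kg). The prespecified range still stops the uncorrected mean being read as device bias.

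**The drink adjustment could matter more.** Section 2.4 leaves its direction unclear. With up to 500 ml drunk, the wrong sign would shift the reference by up to 2 × 500 = 1000 g. That is a separate issue. L is present however drinking is handled, but a correction for L applied to a reference with the wrong drink sign would mean nothing.

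**Conclusion.** The point holds. Followed as written, the plan uses a reference that overstates sweat by respiratory water plus net gas mass, and this shifts the only planned output in one direction. The omission is shown by the text. Its size, roughly 30-170 g per session with a middle near 80 g, is not: it rests on assumed ventilation, exhaled-air temperature, O2 uptake, exchange ratio and body-mass scaling.

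A reader might infer that the device's results are wrong by about 80 g, or that the weight reference is unusable. The documents support neither. They contain no results, no calibration statement and no sweat volume, and weight loss remains a valid reference for agreement with mass loss. A reader might also infer that three fixed subtractions would recover the true error distribution. They would not, because they move its centre only.

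Severity is minor to moderate.

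**What to change.** In section 3:

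1. Keep the uncorrected comparison and label it as agreement with total, drink-corrected mass loss.
2. Add a sensitivity analysis that repeats the 90-minute error distribution after subtracting a prespecified non-sweat loss of 30, 80 and 170 g from the reference, with the assumptions listed.
3. State whether the device output was calibrated to whole-body weight loss, and do not interpret the uncorrected mean error alone as device bias for sweat volume.
4. Set no fixed values for the interim weighings. Section 3 specifies no interim error analysis, and section 2.3 places weighings within breaks and not at set minutes. In the first break the elapsed time could be anywhere from 15 to 25 min, and a time-proportional term would differ by 25/15 − 1 = 67%. If interim errors are analysed, scale the term to the actual weighing time.

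Settle the direction of the drink adjustment in section 2.4 first.

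The cost is a few sentences and three subtractions on data the study already collects, with no new measurement. The downside is that the correction is modelled, is uncertain by more than 5-fold (170/30 = 5.7), and as a constant says nothing about spread. It should therefore be shown as a range beside the uncorrected result and not replace it.

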2.4. Drinking

During the procedure, subjects could drink up to 500 ml of water. The weight of the bottle was measured and recorded after drinking during breaks. The difference was subtracted to the weight loss calculation.

2.5 Restrictions:

In this experiment, we avoided:

1. Urination during test (empty before T0)
2. Weight loss should not exceed 2%

Participants could cancel the experiment at any point of the procedure if desired.

3. Statistical analysis

Data obtained from Spectrophone DBM will be compared to the subject's total weight loss for every participant. The measurement error distribution will be estimated.

Principal investigator

[name]

Signature

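### The planned error distribution alone does not show whether the DBM tracks individual sweat loss or returns a near-constant value

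*Combined protocol and SAP*

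**What the plan says.** Section 3 (Statistical analysis) has two sentences. The first is "Data obtained from Spectrophone DBM will be compared to the subject's total weight loss for every participant". The second is "The measurement error distribution will be estimated". Section 1 defines accuracy in the same terms: it "was defined as the difference between subject weight change during the exertion (due to sweating and water consumption) and the volume of sweat detected" by the DBM. The measure is therefore a difference throughout.

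No acceptance limit, regression slope, correlation, agreement index or reference predictor is named, and the spread of weight loss in the sample is not among the planned results.

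The exercise is close to uniform. Section 2.1 sets four 15-minute treadmill bouts within a 90-minute session, and Section 1 gives a single temperature of 18°C. Under Section 2.2, "Participants could choose high or low intensity of exertion". The two programmes differ by 0.5 km/h at every step; the last step is "0:10-0:15 – 6.5km/h" in the high programme and "0:10-0:15 – 6.0km/h" in the low one. Section 2.3 adds weighings and DBM readings at each break, but Section 3 names only the total loss. Each participant wears two DBMs, one on a Gear S2 and one on a Gear Fit2.

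**The concern.** A distribution of differences describes how far the readings fall from the reference. It does not say whether the reading rises when the reference rises. If everyone does nearly the same work in the same room, a device could sit near the expected average for that work and give unremarkable errors without measuring anything about the individual.

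At stake is what the accuracy result means. A reader will take it as evidence that the DBM measures a person's sweat loss. A report that followed Section 3 exactly could omit everything needed to tell that from reproducing a typical value.

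**Working it through.** **No figure to reproduce.** The documents state no expected loss, SD, accuracy limit or sample-size derivation; 200 is 4 age groups × 50.

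**1. How similar is the exercise?** Inputs are the speeds in Section 2.2, with no distance counted for the 1-minute preparation.
- High: (4×5.5 + 5×6.0 + 5×6.5)/14 = 84.5/14 = 6.04 km/h, or 84.5/60 = 1.408 km per bout and 5.63 km over four.
- Low: (4×5.0 + 5×5.5 + 5×6.0)/14 = 77.5/14 = 5.54 km/h, or 77.5/60 = 1.292 km per bout and 5.17 km over four.
- Ratio: 84.5/77.5 = 1.09.

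If sweat were proportional to distance and the split were 50:50 (both assumptions), programme choice alone would give a CV of (1.408 − 1.292)/(1.408 + 1.292) = 4.3%.

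**2. Algebra.** Let T be true loss, with mean μ and between-person SD σ. The sign convention for the error does not affect its SD.
- Constant monitor showing c = μ: error c − T, bias 0, error SD σ.
- Tracking monitor, reading T plus independent noise of SD σ: error is the noise, bias 0, error SD σ.

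With normal T and normal noise, the two error distributions are identical. What differs is the relation to T: the slope of reading on T is 0 for the first and 1 for the second. None of this depends on the size of σ.

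**3. Simulation at equal error SD.** Assumed: mean 500 g, σ = 100 g, n = 200. A 5% Kolmogorov-Smirnov test on two independent sets of 200 errors separated the monitors in 3.6% of runs, no more than chance. The correlation with true loss separated them clearly: 0.71 (95% range 0.63 to 0.77) for the tracking monitor, and within ±0.14 for a constant with trivial jitter.

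**4. Size under assumed spreads.** Assumed: mean 450 g, σ = 80, 120 or 160 g. For a device with proportional random error of CV k, error SD = k√(450² + σ²).

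| σ (g) | Constant: error SD | 95% limits (1.96σ) | 20% device | 30% device |
|---|---|---|---|---|
| 80 | 80 | ±157 | 91 | 137 |
| 120 | 120 | ±235 | 93 | 140 |
| 160 | 160 | ±314 | 96 | 143 |

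At σ = 80 g the constant has smaller error than both tracking devices. At 120 g it has smaller error than the 30% device only. At 160 g it is worse than both. The ranking turns on σ, which the plan does not ask anyone to report.

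**5. Does a slope settle it?** Take the 20% device at σ = 80 g. Its correlation with true loss is 80/√(80² + 91.4²) = 0.66 and its slope is 1. The approximate standard error of the slope is 91.4/(80×√200) = 0.081, so a 95% CI would be about 0.84 to 1.16, well clear of 0. The slope identifies this device as tracking even though its error SD exceeds that of the constant.

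**The case against.** The strongest reply is that this is a reporting gap and not a design failure. Reference loss and DBM readings are collected for every participant, and a planned comparison does not exclude a slope or a correlation. That stands. A reader might infer that the trial cannot answer whether the DBM measures sweat loss. The documents do not support this: the data can answer it, but the written analysis does not commit to doing so.

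A second reply is that similar walking speed is not similar sweat loss. The study enrols both sexes, four age groups and any body weight. This also stands. A reader might infer that true losses vary little, but no SD is given, and the assumed 80 to 160 g on 450 g is a CV of 18 to 36%, which is not small. Uniform exercise can aggravate the problem; it is not its cause.

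Thirdly, the plan has no decision rule, so nothing in it would declare a constant device accurate. Limits of ±157 to ±314 g on a 450 g mean are ±35% to ±70%, and a careful reader would call that poor. This is fair, but the same limits could come from a noisy device that does track, and the planned output would not say which.

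The break weighings do not rescue the plan as written. Section 3 does not use them, and cumulative loss rises with time in everyone, so a monitor showing one fixed sweat rate would follow them too.

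**Conclusion.** The point holds as a gap in the analysis plan. At any between-person spread, the distribution of differences by itself does not distinguish a DBM that tracks individual loss from one that returns a near-constant value. This part is algebra and rests on no assumed figure.

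The size does rest on assumptions. At a mean of 450 g, a constant reading would show an error SD of 80 to 160 g against 91 to 96 g for a tracking device with 20% error, so it could look better or clearly worse depending on a spread that the documents do not give. The uniform exercise makes a smaller spread more plausible but does not establish one. The remedy is a low-cost addition to Section 3, and the design need not change.

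**What to change.** Add to Section 3, for the Gear S2 and Gear Fit2 DBMs separately, beside bias and 95% limits of agreement:

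- (a) The mean and SD of water-corrected reference weight loss, so that the error SD can be read against the spread.
- (b) The slope of DBM reading on reference loss with its 95% CI. State that the DBM tracks individual sweat loss only if the CI excludes 0 (in the positive direction), and report departure from 1 as proportional bias.
- (c) Descriptively, the ratio of DBM RMSE to the leave-one-out RMSE of a prediction from baseline weight and chosen intensity, with a bootstrap 95% CI.

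A concordance correlation may be added as a supplement.

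Item (c) should carry no pass/fail threshold. Requiring the upper bound of the ratio to be below 1 would fail devices that do track. At σ = 80 g the 20% device has a ratio of at least 91.4/80 = 1.14 and passed in 0% of simulated trials, despite a slope of 1.0. At σ = 120 g it passed in about 97%, 66% or 6% of trials when the predictors explained 0%, 20% or 40% of the variance in loss.

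The cost is one paragraph and a little more analysis, with no new data. The only downside is that an accuracy statement becomes harder to earn.

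### Section 3 never relates the DBM's error to body weight, so a weight-related error, if present, could offset in the mean and pass as random scatter

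*Combined protocol and SAP*

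**What the plan says.** Section 1 puts a DBM on each wrist: one under the Gear S2 on the right, the other under the Gear Fit2, which was "attached to the bottom of the band was placed on the left wrist of the participant". The reference is whole-body: "subject weight was also monitored using commercially available digital balancers". Accuracy is taken to be "the difference between subject weight change during the exertion (due to sweating and water consumption) and the volume of sweat detected by Spectrophon DBM". This is an absolute amount, not scaled to the person.

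Body weight is available for everyone. Section 2 states: "Participants were weighed prior to the experiment (no clothing after maximal drying"). Section 2.3 repeats the weighing at each break.

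Section 3 has two sentences. The first compares DBM data with total weight loss for every participant. The second reads "The measurement error distribution will be estimated". It names no covariate, regression, weight stratum or percentage scale. The only weight-relative figure in the document is the 2% limit in Section 2.5, which governs conduct and is not an analysis. The eligibility criteria set no limit on weight or BMI.

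**The concern.** A local wrist reading can match a whole-body loss only through some conversion, explicit or built in. The documents do not describe it, and they do not say whether the wearer's weight is an input.

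The design makes body size a natural place to look for a fault. Everyone walks one of two similar fixed-speed programmes, and at equal speed whole-body sweat can be expected to rise with body mass. If the conversion does not follow that rise, lighter users would be over-read and heavier users under-read, or the reverse if it over-corrects. The two can offset in the mean error. What remains is extra spread, and a single error distribution cannot show whether that spread is random or could be predicted from weight and corrected.

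At stake is whether the accuracy statement applies to an individual user, who knows their weight before putting the device on.

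**Working it through.** **Figures in the plan.** The sample size agrees with its parts: 4 age bands x 50 = 200. The plan gives no SD, margin, power or precision figure, so there is nothing else to reproduce.

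**How close the two programmes are (Section 2.2, 14 walking minutes).** High: (4 x 5.5 + 5 x 6.0 + 5 x 6.5)/14 = 6.04 km/h. Low: (4 x 5.0 + 5 x 5.5 + 5 x 6.0)/14 = 5.54 km/h.

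**Illustration. Every input below is an assumption, because the documents give none.**
- Body weight W: mean 75 kg, SD 12 kg.
- True loss S: proportional to W, with mean 300 or 600 g and person-to-person CV 25%.
- Device reading: c x S x (W/75)^(-b). Here b is the power by which the conversion misses body size, and c is set so that the pooled mean error is zero.
- Other error: SD 10% or 30% of mean sweat.
- Error: device minus reference.

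**Mean error at weight w** = c x (w/75)^(-b) - 1, with c approximately 1/[1 - b(1-b)/2 x (12/75)^2]. This gives c = 1.0027, 1.0032 and 1 for b = 0.3, 0.5 and 1.0.
- 60 kg: 1.0027 x 0.8^(-0.3) = 1.072; 1.0032 x 0.8^(-0.5) = 1.122; 0.8^(-1) = 1.25.
- 90 kg: 1.0027 x 1.2^(-0.3) = 0.949; 1.0032 x 1.2^(-0.5) = 0.916; 1.2^(-1) = 0.833.

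The 55 and 100 kg rows below use the same formula. Coverage is the share of errors inside the pooled mean +/- 1.96 SD, by simulation.

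| | b = 0.3 | b = 0.5 | b = 1.0 |
|---|---|---|---|
| Mean error at 55 kg | +10% | +17% | +36% |
| Mean error at 60 kg | +7% | +12% | +25% |
| Mean error at 90 kg | -5% | -8% | -17% |
| Mean error at 100 kg | -8% | -13% | -25% |
| Coverage at 55 kg, other error 10% | 92% | 89% | 82% |
| Coverage at 60 kg, other error 10% | 94% | 93% | 94% |
| Coverage at 90 kg, other error 10% | 94% | 93% | 94% |
| Coverage at 100 kg, other error 10% | 86% | 76% | 64% |
| Coverage at 55 kg, other error 30% | 94.5% | 94% | 90% |
| Coverage at 100 kg, other error 30% | 94% | 92% | 86% |
| Error variance explained by weight, other error 10% | 18% | 37% | 69% |

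With 10% other error, coverage at 75 kg is 97% to 100%, so the pooled range is too wide there. With weight SD 15 kg, coverage at 100 kg is 88%, 83% and 81%. With b = 0, every mean error is zero and coverage is nominal.

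**In grams**, with mean sweat 600 g, the true mean is 480 g at 60 kg and 720 g at 90 kg. The bias is then about +35 g (0.072 x 480) to +120 g (0.25 x 480) at 60 kg, and about -37 g (0.051 x 720) to -120 g (0.167 x 720) at 90 kg. With mean sweat 300 g, halve these.

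**A second, simpler model.** Suppose the reading does not vary with weight, loss is 1% of weight, weight SD is 15 kg and random SD is 100 mL. The slope is -10 mL/kg and the pooled SD is sqrt((10 x 15)^2 + 100^2) = 180 mL. In 5,000 simulated trials of 200, the pooled mean error was about 0, the lightest third over-read by about 162 mL and the heaviest third under-read by the same. The 95% limits are +/-353 mL pooled and +/-196 mL at a fixed weight. The pattern is hidden in the mean but not in the spread.

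**Is n = 200 enough?** The detectable correlation between error and weight at 80% power is tanh((1.96 + 0.84)/sqrt(197)) = 0.20. In the first model with mean sweat 600 g, the slopes are -2.4, -4.0 and -8.0 g/kg. Their SE, residual SD/(12 x sqrt(200)), is 0.36 to 0.38 with 10% other error, so power is near 100%. With 30% other error the SE is about 1.07, and power is about 60% at b = 0.3 and 96% at b = 0.5.

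**The case against.** The strongest objection is that the premise is not in the documents. The conversion is unseen, and it may already use body weight correctly. The zero pooled mean is built into the illustration by the centring and is not a finding. Both points stand. The calculation shows what is possible, not what is so.

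A reader might infer that the DBM is biased by body size, or that a pooled 95% range would mislead light and heavy users generally. The documents support neither. They contain no evidence of a body-size error, and its direction could be the reverse. Even under the assumed model, the range is near nominal at 60 and 90 kg, roughly the 10th and 90th percentiles. The poor coverage is at 100 kg, a weight that about 1.9% of people reach under the assumed distribution (about 4 of 200), and it largely goes when other error is 30%, except at b = 1.0.

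A further point is that Section 3 commits to neither a mean error nor a 95% range, and that a wide distribution would itself reveal poor accuracy. That is fair, but the distribution cannot show that part of its width is predictable from weight.

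Nor is baseline weight structurally independent of the error: it is the first term of the weight-loss reference. The coupling should be negligible if scale error is in grams and weight varies between people by kilograms.

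Finally, the same argument could be made for skin properties, fitness or wrist fit. Body weight differs in being recorded already, known to the user beforehand, and expected to drive the whole-body reference.

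**Conclusion.** The point holds as a gap in the analysis, not as a demonstrated defect of the device. The plan judges a wrist reading against whole-body loss, records body weight in everyone, sets no weight limit, and never relates the error to weight. If the device does not allow for body size correctly, systematic error can offset in the mean and be read as random.

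Under the assumed inputs the main loss is the unseen mean bias: about +7% to +25% at 60 kg and -5% to -17% at 90 kg, with a pooled mean of zero. Miscoverage of the pooled range is a secondary matter, confined mainly to the extremes and to small other error. All these sizes depend on assumed weight, sweat and noise figures and on b between 0.3 and 1.0; at b = 0 nothing is lost. A slope near zero with a tight interval would also be useful, since it would support the pooled statement.

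**What to change.** Add to Section 3:

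> For each carrier (S2, Fit2), regress the participant's error (DBM sweat volume minus weight-loss reference), in grams and as % of reference loss, on baseline nude body weight, without and with adjustment for sex. Always report the slope with 95% CI and the predicted mean error and 95% range at the 10th, 50th and 90th percentiles of body weight, alongside the pooled error distribution, allowing the error spread to vary with weight.

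Reporting should not depend on the slope's significance. At b = 0.3 with 30% other error, power is about 60%, so such a rule would fall back on the pooled range about 40% of the time despite a real bias. It could also give the two carriers different reporting formats.

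The sex-adjusted fit is needed because weight and sex are mixed in the unadjusted slope. Read a non-zero slope as weight-related error, not as proof of a conversion fault.

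The cost is a short addition to Section 3 and a few regressions per carrier on data the plan already collects, with no new participant, visit or measurement. The downside is a slightly longer report and possibly a less favourable accuracy statement for light or heavy users.
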